7.5.2 Subject Follow-up for OS

Overall Survival probabilities for each subpopulations will be estimated and plotted using the Extent of follow-up defined as the time between first dose date and last known date alive (for subjects who are alive) or death date (for subjects who died) will be summarized descriptively (median, min, max) for all subjects treated.

The currentness of follow-up, defined as the time between last OS contact (ie, last known date alive or death date) and data cut-off date, will be summarized by subpopulations. Subjects who died before data cut-off date will automatically have zero value for currentness of follow-up. For subjects with last known date alive after data cut-off date, they will have zero value for currentness of follow-up as well. The currentness of follow-up will be categorized into the following categories: 0 days, 1-30 days, 31-60 days, 61-90 days, 91-120 days, 121-150 days, 151 or more days.

7.5.3 Subgroups Analyses

OS among treated population will also be summarized within subsets at baseline (with two-sided 95% CI for the medians calculated via log-log transformation.).

- Age (< 65, ≥ 65)
- Gender (male, female)
- M-Stage at diagnosis
- Number of lines of prior systemic treatment in metastatic setting (add footnote for only metastatic setting)
- Baseline LDH (≤ ULN, >ULN, >2xULN)

7.6 Safety

Unless otherwise specified, safety results will be presented using the all treated analysis set subjects by subpopulations. See Core Safety SAP for more details on safety analysis.

7.6.1 Primary Analysis

7.6.1.1 High-grade (CTCAE v4.0 Grade 3 or higher) Treatment-Related, Select Adverse Events.

The number and percentage of subjects who report high-grade (CTCAE v4.0 Grade 3 or higher), treatment-related, select adverse events pulmonary, gastrointestinal, skin, renal, hepatic, pancreatic, neurologic, endocrine) will be summarized using the all treated analysis set by system organ class and Medical Dictionary for Regulatory (MedDRA) preferred term. In addition, the number, percentage of subjects, 95% CI for the percentage of subjects with these select AEs will also be presented by subpopulations.

7.6.2 Secondary Analysis

7.6.2.1 High-grade (CTCAE v4.0 Grade 3 or higher) Select Adverse Events

The number and percentage of subjects who report high-grade (CTCAE v4.0 Grade 3 or higher), select adverse events will be summarized using the all treated analysis set by system organ class and Medical Dictionary for Regulatory (MedDRA) preferred term.

7.6.2.2 Select Adverse Events

Select adverse events will be summarized according to their incidence, as well as their time to onset and resolution as described in Section 7.6.6 of the Core Safety SAP.

7.6.3 Other Safety Analysis

Other safety analysis will be conducted as below as specified in the Core Safety SAP, according to the general methods:

- Deaths
- Serious adverse events
- Adverse events leading to discontinuation of study therapy
- Adverse events leading to dose modification
- Adverse events
- Multiple adverse events
- Laboratory parameters
- Vital signs
- Pregnancy
- Adverse events by demographic subgroups

A summary by type of autoimmune disorder will be presented for the following adverse events tables.

- Any adverse events
- Drug-related adverse events
- Drug-related serious adverse events
- Drug-related adverse events leading to discontinuation
- Drug-related select adverse events
- Drug-related select adverse events leading to discontinuation
- Any adverse events that required immune modulating medications
- Time to resolution of drug-related select adverse events
- Time to resolution of drug-related select adverse events where immune modulating medications was initiated
- Time to onset of drug-related select adverse events

■ [REDACTED]

A subject listing of prior immune modulating medications (subjects with any prior immune modulating medication, subjects by medication class and generic term) will be presented. This would include immune modulating medications taken on or before first dose of study therapy.

7.6.4 Immunogenicity Analysis

Not applicable

7.8 Outcomes Research Analyses

■ [REDACTED]

■ [REDACTED]

Outcomes research (Quality-of-life) data will be measured using the EORTC QLQ-C30 and EQ-5D-3L questionnaires. The analysis of EORTC QLQ-C30 and EQ-5D-3L will be restricted to treated subjects who have an assessment at baseline and at least one post-baseline assessment.

7.8.1 EORTC QLQ-C30

For EORTC QLQ-C30, all scales and single items are scored on categorical scales and linearly transformed to 0-to-100 scales with higher scores for a functional scale representing higher levels of functioning, higher scores for the global health status/quality of life scale representing higher levels of global health status/quality of life and higher scores for a symptom scale representing higher level of symptoms. A score difference of 10 is used as an estimate of a clinically important difference for the scales of the EORTC QLQ-C30⁵.

The following descriptive analyses will be conducted:

- EORTC QLQ-C30 questionnaire completion rate, defined as the proportion of questionnaires actually received out of the expected number (i.e., number of subjects on treatment or in follow up) will be calculated and summarized for each assessment time point by treatment group.

- Mean score and mean change from baseline in EORTC QLQ-C30 global health status, functional scales and symptom scales will be summarized using descriptive statistics (N, mean with SD and 95% CI, median, first and third quartiles, minimum, maximum) for all scales at each assessment time point.
- A line graph summarizing the mean changes from baseline will be produced for all scales.

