Laboratory Tests	X		X (TFTs only)	CBCs with differential, ^a Serum chemistry tests, ^b liver function tests ^c and lipase should be checked every cycle, and the results should be obtained prior to dosing. TFTs ^d should be checked every 3 cycles (every 6 weeks) starting with Cycle 1. May be completed more frequently if required by local standards. Laboratory tests should be completed 72 hours prior to dosing, and the results must be available prior to dosing. See footnote b regarding availability of lipase results prior to dosing.
Pregnancy Test		X		Completed every 2 cycles, starting with Cycle 1. May be completed more frequently if required by local standards

Table 5.1-2: CA209172 On-Treatment Assessments

Procedure	Each Cycle (every 2 weeks) (±2 days)	Every 2 Cycles (every 4 weeks) (±2 days)	Every 3 Cycles (every 6 weeks) (±2 days)	Notes
Efficacy Assessments				
Tumor Scans	---	---see notes---		Mandatory initial tumor assessment is to be completed at Week 12 (±5 days). If known or new CNS metastases are detected during screening, a brain scan is required at the mandatory tumor assessment at Week 12 (±5 days). Further tumor assessments are recommended to be completed as required by local standards of care or at the investigator's discretion and are recommended every 8 weeks. The assessment of clinical benefit should be balanced by clinical judgment as to whether the patient is clinical deteriorating and unlikely to receive any benefit from continued treatment with nivolumab.
Survival	X			
Outcomes Assessments				
EQ-5D-3L		X		Every 2 cycles (4 weeks) for 4 months starting with Cycle 1, then every 4 cycles (8 weeks) after first administration of nivolumab prior to any study procedures and treatments
EORTC QLQ-C30		X		Every 2 cycles (4 weeks) for 4 months starting with Cycle 1, then every 4 cycles (8 weeks) after first administration of nivolumab prior to any study procedures and treatments
Clinical Drug Supplies				
Administration of Study Drug	X			

BP = blood pressure; CBC = complete blood count; HR = heart rate; LDH = lactate dehydrogenase; LFT = liver function test; NCI CTCAE = National Cancer Institute Common Terminology Criteria for AEs; O2 = oxygen; PS = Performance Status; RR = respiratory rate; TFT, thyroid function test.

^a CBCs with differential includes white blood cell count, lymphocyte count, absolute neutrophil count, hemoglobin, hematocrit, and platelet count. Results to be obtained prior to dosing on infusion days

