- b Serum chemistry tests include blood urea nitrogen [BUN] or serum urea level, serum creatinine, sodium, calcium, chloride, lipase, and glucose. Amylase should be performed in addition to lipase in cases where lipase results are not available prior to dosing.
- c Liver function tests include AST, ALT, total bilirubin, alkaline phosphatase, albumin.
- d Thyroid function testing including TSH (free T3 and free T4 if abnormal results for TSH).

Table 5.1-3: Off-Treatment Follow-Up Assessments:CA209172

Procedure	Every 4 Weeks	FU-X01 (30 days ±7 days)	FU-X02 (70-84 days after FU- X01 ±7 days)	Follow-Up After X01 and X02. Every 3 months. (±7 days)	Notes
Safety Assessments					
Physical Examinations		X	X		Collect weight and ECOG PS. Focused physical examination may be performed if clinically indicated.
Vital Signs and Oxygen Saturation		X	X		Temperature, BP, HR, RR, O2 saturation by pulse oximetry at rest (also monitor amount of supplemental oxygen if applicable) prior to dosing and at any time a patient has any new or worsening respiratory symptoms.
Adverse Events Assessments		X	X		Beyond 100 days from the last dose of study therapy, patients followed for ongoing drug-related adverse events until resolved, symptoms return to baseline or are deemed irreversible, lost to follow-up, or withdrawal of study consent.
		■	■		
Laboratory Tests		X	X		Serum chemistry tests and TFTs should be checked at FU1 and FU2.
Pregnancy Test	X	X	X		Pregnancy testing may be performed at home if an in-office visit is otherwise not required.
Efficacy Assessments					
Tumor Scans				-----see notes-----	Tumor progression scans are recommended to be completed as required by local standards of care or at the investigator's discretion.

Table 5.1-3: Off-Treatment Follow-Up Assessments:CA209172

Procedure	Every 4 Weeks	FU-X01 (30 days ±7 days)	FU-X02 (70-84 days after FU- X01 ±7 days)	Follow-Up After X01 and X02. Every 3 months. (±7 days)	Notes
Survival Follow-up		X	X	X ^a	
Outcomes Assessments					
EQ-5D-3L		X	X	X ^a	The EQ-5D-3L can be completed by mail, e-mail, or telephone call (using the telephone version) when a clinical visit is not otherwise required. When a clinical visit is required, the questionnaire should be completed at the clinic.

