8.2 Populations for Analyses

- The safety analysis set comprises patients who received at least 1 dose of nivolumab. The analysis of safety, OS, and QoL data will be based on the safety analysis set.
- The response evaluable analysis set comprises patients who received at least 1 dose of nivolumab and have both baseline and at least 1 post-baseline tumor scan.

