Amendment 02	16-Jan-2015	
 The inclusion criteria have been expanded and the exclusion criteria have been minimized. [REDACTED] The options for palliative local therapy have also been expanded to meet the needs of the current subject populations. The EORTC QLQ-C30 has been eliminated from the subject follow up. The time points and frequency of assessments have been updated. The subjects in Cohort 2 will now be analyzed at the same frequency to Cohort 1, so the separate Time and Events Schedule for Cohort 2 was removed. The statistical section has been reformatted to aid understanding of the analyses to support the respective primary, secondary, and [REDACTED] objectives. The timing and frequency of all assessments have been removed from sections of the protocol outside of the Time and Events tables. The endpoints are more representative of the data that will be collected in support of the objectives. The requirement for electrocardiograms has been removed.
Administrative Letter 03	02-Oct-2014	
 Correct the tables in Section 5.1, Flow Chart/Time and Events Schedule so that the information in these tables is consistent with the text in the protocol.
Revised Protocol 01a	04-Jun-2014	
 Incorporates Administrative Letter 01, Administrative Letter 02, and Amendment 01.
Amendment 01	04-Jun-2014	
 Revisions aim to comply with the Health Authority requirements in Germany

Table 2: Protocol Amendments

Document	Date	Summary of Changes
Administrative Letter 02	21-May-2014	
 A number was missing from Exclusion Criterion 4cviii. This letter is to provide you with the missing number. This is an administrative protocol change and does not significantly affect the safety of subjects, study scope, or scientific quality of a Phase Iib. Accordingly, it may be implemented immediately.
Administrative Letter 01	12-May-2014	
 The title of this protocol has been modified for consistency with the BMS conventions for protocols in the nivolumab program. This is an administrative protocol change and does not significantly affect the safety of subjects, study scope, or scientific quality of a Phase II or III protocol. Accordingly, it may be implemented immediately.
Original Protocol	18-Apr-2014	Original Protocol

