4.2.1 Incidence of all High-grade, Select AEs

The incidence for high-grade (CTCAE v4.0 Grade 3 or higher), select adverse events. The select Adverse Events consist of a list of preferred terms grouped by specific category as follows:

- Pulmonary toxicity
- Gastrointestinal toxicity (diarrhea or colitis)
- Endocrinopathies
- Hepatotoxicity (including asymptomatic LFT elevations)
- Renal toxicity
- Skin toxicity
- Hypersensitivity/Infusion site reaction

[Redacted]

- [Redacted]
- [Redacted]
- [Redacted]
- [Redacted]
- [Redacted]

[Redacted]

- [Redacted]

[Redacted]

- [Redacted]
- [Redacted]
- [Redacted]
- [Redacted]
- [Redacted]
- [Redacted]
- [Redacted]
- [Redacted]
- [Redacted]

[Redacted]

[Redacted]

Table 3: Time Windows for Assessments

Nominal Time-Point	Time Window
Week 1 (Baseline)	Prior to first dose on Day 1
Week 5	Day 2 thru Day 55, inclusive
Every 4 weeks up to Week 13	Nominal day (+26 days/-2 days, inclusive)
Week 17	Nominal day 113 (+54 days/-2 days, inclusive)
Every 8 weeks thereafter	Nominal day (+54 days/-2 days, inclusive)
Follow-up 1 (EQ-5D-3L only)	If assessment is post last dose and within 30 days of last dose (+68-82 days/-2 days, inclusive)
Follow-up 2 (EQ-5D-3L only)	If assessment is post 70-84 days of Follow-up 1 (+89 days/-2 days, inclusive)
Every 3 months thereafter (EQ-5D-3L only)	If assessment is after Follow-up 1 and Follow-up 2 (+89 days/-2 days, inclusive)

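### The SAP's QLQ-C30 completion rate counts follow-up subjects who are no longer due the form, and SAP 7.8 separately narrows the QoL set against the protocol; the two errors pull in opposite directions

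*SAP*

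**What the plan says.** **Denominator.** SAP 7.8.1 defines the QLQ-C30 completion rate, for each assessment time point, as the "proportion of questionnaires actually received out of the expected number (i.e., number of subjects on treatment or in follow up". SAP 7.8.2 uses the same definition for the EQ-5D-3L.

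**Schedule.** The QLQ-C30 appears at Visit 1 (protocol Table 5.1-1) and in the on-treatment Table 5.1-2: "Every 2 cycles (4 weeks) for 4 months starting with Cycle 1, then every 4 cycles (8 weeks". The off-treatment Table 5.1-3 has no QLQ-C30 row. Its only questionnaire is the EQ-5D-3L, with the note "The EQ-5D-3L can be completed by mail, e-mail, or telephone call". SAP Table 3 labels its first follow-up window "Follow-up 1 (EQ-5D-3L only" and restricts the other two follow-up windows in the same way. The amendment history in SAP 2.4 fits this: "The EORTC QLQ-C30 has been eliminated from the subject follow up".

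**Analysis set.** SAP 7.8 states that analysis of both questionnaires is "restricted to treated subjects who have an assessment at baseline and at least one post-baseline assessment" and makes no exception for completion rates or baseline summaries. Protocol 8.2 says: "The analysis of safety, OS, and QoL data will be based on the safety analysis set". Protocol 8.4.6 repeats the full safety analysis set for the summaries at each time point. That set requires one dose of nivolumab and has no questionnaire condition.

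**The concern.** Readers use the completion rate to judge how far the QoL means can be trusted, so its denominator should be the subjects who were due the form.

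Follow-up starts when the decision to stop nivolumab is made (protocol 3.1, SAP 2.1). A subject who stops early is therefore in follow-up while others reach later on-treatment visits. Under 7.8.1 that subject adds to the denominator of those visits and cannot add to the numerator.

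The set in 7.8 works the other way. It admits only subjects who returned a baseline form and a later one, so subjects who die or stop responding before a second form are not counted. They also leave the baseline means, which the protocol intends to describe all treated patients.

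At stake is a descriptive compliance table and the baseline QoL description. No test and no safety conclusion depends on them.

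**Working it through.** The documents state no completion rate, discontinuation rate or follow-up share, so there is no planned figure to reproduce. The schedules, the set definitions and the total of about 800 treated patients (protocol section 8) come from the documents. Every other input below is an assumption chosen to show direction.

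**Step 1: denominator rule alone.** Let c be completion among subjects on treatment. Then reported rate = c × on-treatment ÷ (on-treatment + follow-up), with both shares taken as fractions of all treated subjects.

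| Assumed on treatment | Assumed in follow-up | Reported if c = 100% | Reported if c = 85% |
|---|---|---|---|
| 60% | 30% | 0.60/0.90 = 67% | 57% |
| 45% | 35% | 0.45/0.80 = 56% | 48% |
| 30% | 40% | 0.30/0.70 = 43% | 36% |

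With the denominator limited to subjects on treatment, each row would report c itself.

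**Step 2: analysis-set rule alone.** Every member of the 7.8 set has a baseline form by definition, so baseline completion is 100% whatever the true value. Let b be true baseline completion and q the share of those subjects with a later form. Set size = 800 × b × q.

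- b = 70%, q = 60%: 800 × 0.70 × 0.60 = 336 in the set, 464 left out.
- b = 95%, q = 90%: 800 × 0.95 × 0.90 = 684 in the set, 116 left out.

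**Step 3: both rules together.** Assumed counts:

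- Week 5: 720 on treatment, 60 in follow-up, 560 forms received. Within the 7.8 set: 620 on treatment, 10 in follow-up, 550 forms.
- Week 49: 250 on treatment, 250 in follow-up, 210 forms received. Within the 7.8 set: 235 on treatment, 180 in follow-up, 208 forms.

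| Rate | Week 5 | Week 49 |
|---|---|---|
| Subjects due the form | 560/720 = 77.8% | 210/250 = 84.0% |
| Follow-up counted, all treated | 560/780 = 71.8% | 210/500 = 42.0% |
| 7.8 set, on treatment only | 550/620 = 88.7% | 208/235 = 88.5% |
| Both rules as written | 550/630 = 87.3% | 208/415 = 50.1% |

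In this example the net error is 87.3 − 77.8 = +9.5 points at Week 5 and 50.1 − 84.0 = −33.9 points at Week 49. Completion among subjects due the form rises between the two visits, while the rate as written falls.

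**The case against.** **The follow-up clause may be empty for the QLQ-C30.** SAP Table 3 gives this questionnaire no follow-up time points, and the phrase fits 7.8.2, so 7.8.1 looks like carried-over wording. A programmer working from Table 3 might ignore it. That is a plausible account of how the wording arose, but 7.8.1 does not say it, and a definition should not depend on a programmer discarding half of it. SAP sections 8 and 9 defer further conventions and output details to a Data Presentation Plan that is not among the documents, so it cannot be said that the final tables will be wrong.

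**Section 7.8 may not be meant to govern completion.** If 7.8.1 supplies its own denominator, baseline completion is not forced to 100%. This is fair, and the 100% result is conditional on 7.8 applying. The follow-up error then remains in full, and so does the conflict with the protocol over the baseline means.

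**SAP 8.4 bases outcomes analyses on all available data and plans pattern mixture models.** That section deals with missing values and imputation. It does not restore the subjects whom 7.8 excludes; if anything it sits awkwardly with 7.8.

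**Stronger readings that the documents do not support.**

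- A reader might infer that completion will be too low at every visit after baseline. With both rules applied, the Week 5 example is too high.
- A reader might infer that follow-up subjects never had the form. They were due it at baseline and on treatment; they are not due it once in follow-up.
- A reader might infer that the excluded subjects are the sickest. Early deaths would be among them, but the documents neither show nor size this.

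**Conclusion.** The point stands on the text. SAP 7.8.1 counts as expected responders subjects who are not due the QLQ-C30, and SAP 7.8 sets a narrower QoL population than protocol 8.2 and 8.4.6.

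The first rule can only lower the rate, increasingly as subjects leave treatment. The second, if it governs completion, fixes baseline at 100% and raises early rates; in any case it takes subjects without a second form out of the baseline means. The two do not cancel in general, and the net direction depends on the visit.

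The size cannot be derived from the documents. The 43%-67% range covers the denominator rule alone under assumed shares, and the Week 5 and Week 49 rates rest on assumed counts. Neither is a forecast.

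The correction should be made, but its weight is moderate: QoL is not among the legible primary or secondary endpoints, and the measure is descriptive.

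**What to change.** 1. In SAP 7.8.1, define expected QLQ-C30 forms at a time point as treated subjects who are alive, on treatment and scheduled for the form at that time point. Remove the follow-up clause there and keep it in 7.8.2 for the EQ-5D-3L only.
2. In SAP 7.8, state that completion rates and the baseline and visit summaries for both questionnaires use all treated subjects, and that the requirement for a baseline and a later form applies only to change from baseline. This brings the SAP into line with protocol 8.2 and 8.4.6.

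The cost is two SAP sentences and matching denominators in the tables. No new data are needed.

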7.8.2 EuroQoL Five Dimensions Questionnaire

The following descriptive analyses will be conducted:

- EQ-5D-3L questionnaire completion rate, defined as the proportion of questionnaires actually received out of the expected number (i.e. number of subjects on treatment or in follow up), will be calculated and summarized for each assessment time point by treatment group.
- A by-subject listing of the level of problems in each dimension, corresponding to EQ-5D-3L health state (i.e., 5-digit vector), EQ-5D-3L utility index score, and EQ-5D-3L VAS score will be provided.
- Proportion of subjects reporting problems for the 5 EQ-5D-3L dimensions at each assessment time point will be summarized by level of problem and by treatment group. Percentages will be based on number of subjects assessed at assessment time point.
- For the EQ-5D-3L utility index and VAS scores, separately:
 - Mean score and mean change from baseline at each assessment time point will be summarized by treatment group using descriptive statistics (N, mean with SD and 95% CI, median, first and third quartiles, minimum, maximum).
 - A line graph summarizing the mean changes from baseline will be produced.

8 CONVENTIONS

Unless otherwise noted, the following conventions should be understood to apply. Further conventions may be detailed in the Data Presentation Plan (DPP).

8.1 Baseline

Baseline results will be the last non-missing result occurring prior to the first dose of treatment medication.

